Milestone 1: NF loci (dACC or amygdala) must show higher activity during ESF-NF and higher FC with mPFC after NF training during the ESOM or ER tasks with effect sizes of $d \geq 0.4$.

Milestone 2: 20% of variance in psychological target's change (ETB, IAT) must be associated with amygdala or dACC to mPFC FC changes during the ESOM or ER tasks after NF.

If those milestones are met, during **the R33 phase**, 70 suicide attempting participants with pre-NF assessments will be randomized 1:1 to: NF or NF from a region that is not related to memory recall, labeled as "Unrelated-NF". Participants will be matched in sex, age, IQ, illness severity, suicide ideation, and abuse history if possible. Leveraging Bayesian methods to increase power, our aims and hypothesis (**H**) for the R33 phase are:

R33 Aim 1. Confirm target engagement in the NF versus the Unrelated-NF group.

H1.1: Right amygdala or dACC activity will be higher for active versus Unrelated-NF.

H1.2: Right amygdala or dACC – mPFC FC will be higher during self-processing and affect regulation tasks following active NF compared to Unrelated-NF training sessions.

R33 Aim 2. Test the relationship between neural and psychological targets' engagement and suicide ideation. H2.1: Lower affect dysregulation and abnormal self-processing behavior will follow active NF as compared to Unrelated-NF, mediated by amygdala or dACC to mPFC FC changes in self-processing and affect regulation tasks. H2.2: Higher amygdala or dACC to mPFC FC after NF will be associated with lower suicide ideation. H2.3: Affect dysregulation or abnormal self-processing behavioral changes will mediate the association between changes in FC and suicide ideation before versus after NF.

2. Background

Suicide is the 2nd leading cause of adolescent death in the U.S ²¹. Yet it is increasingly acknowledged that current evidence-based interventions for illnesses linked to suicide ideation and attempts underperform across the lifespan ^{1-7,22}.

3. Study Endpoints/Events/Outcomes

3.1 Primary Endpoint/Event/Outcome:

The primary outcome of the R61 stage will be the fMRI imaging results, behavioral tasks (IAT and EBT) and self-reported suicide ideation data. The DERS²³, RD¹²⁰ and the SPPA^{24,25} will provide self-report measures of affect dysregulation and abnormal self-processing. **The primary outcomes of the R33 stage** are similar as above but now include the C-SSRS⁹⁸ and SIQ²⁹ to test changes in suicide ideation and attempts

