1. **Safety Plan:** Able to cooperate with the (Stanley & Brown, 2012) Safety Plan. Additional positive criteria include details and accessibility of means and persons to enact it. Participants should be able to provide the name of an adult that they can contact if suicide ideation escalates. Additionally, participants should be able to name specific activities or de-escalating regulatory actions to cope with elevated suicide ideation. The credibility of the suicide plan is often indicated by levels of specificity and elaborations in the coping strategies provided. Evaluating a safety plan specificity is a subjective judgment, therefore the ability to cooperate to create a plan is more important than its level of detail as the latter may depend on verbal and communication skills that do not indicate willingness or ability to follow a safety plan.

2. **C-SSRS:** Any suicide ideation severity yielded by the (C-SSRS, ⁴⁹), Scores 0-5-.

Category 0 – Absent suicide ideation or attempts
 Category 1 – Wish to be Dead
 Category 2 – Non-specific Active Suicidal Thoughts
 Category 3 – Active Suicidal Ideation with Any Methods (Not Plan) without Intent to Act
 Category 4 – Active Suicidal Ideation with Some Intent to Act, without Specific Plan

Category 5 – Active Suicidal Ideation with Specific Plan and Intent
 Category 6 – Preparatory Acts or Behavior
 Category 7 – Aborted Attempt
 Category 8 – Interrupted Attempt
 Category 9 – Actual Attempt (non-fatal).
Category 10–Completed Attempt (fatal)

3. **Caregivers/parents or adult participants statement of responsibility:** If C-SSRS yields scores of 4 or 5 or higher but parents or caregivers or adult participants state that they can keep the participants safe at home.

4. **Participants statement:** Participants can commit to not attempting suicide between the present and the next research encounter.

5. **Suicide means and psychoeducation.** Low to moderate risks during evaluation of access to suicide means.

6. **Recommendation to parents** and additional measures to ensure safety of enrolled participants

- Caregiver(s) will be recommended to increase the level of care with existing providers or seek them if currently absent. Referrals to the U of M outpatient clinic will be provided to the participants and the caregiver.

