- [name] (or the designated psychiatrist or accredited mental health professional) will increase contact with participants/family (call and talk to participants 1 or 2 times a week as needed), particularly if staff becomes aware of periods of high stress, family chaos, increased difficulties at school, bullying, losses, or transitions in care.

- **Document:** risk and protective factors assessment, safety plans, rationale for level of intervention/care.
- When in doubt – consult [name] or the designated pediatric psychiatrist.
- Consult with other providers in the department of psychiatry

7. The Dialectical Behavioral Therapy (DBT: [contact]) team can be consulted via email 2 weeks before the visit with copy to the PI: [contact]

16.5 Exclusion and triage of in person suicide risks. Risk factors are cumulative, the presence of one risk factor does not automatically exclude a participant. The presence of many risk factors and the absence of protective factors, however, merits considering exclusion from the research.

Exclusion and referral for increased outpatient level of care or emergency department (ED) assessment for hospitalization if:

- Scores of **4 or 5** or higher in the C-SSRS (Category 4 - 6) and:
 - **Caregivers are unable or unwilling to keep the participants safe at home.**
 - Participants show uncertainty (i.e., cannot promise not to attempt suicide) about not attempting suicide between the present and the next research session.
- Inability to fashion a credible Stanley & Brown Safety Plan.

[figure not shown]
- Determination of high chronic or acute risk due to presence of multiple risk factors and absence of protective factors: e.g., access to suicide means and unreliable or absent control over them.
- In consultation with the “on call” PI or pediatric psychologist this could result in referral for increased levels of current established care or escorting the participants and family to the emergency department (ED) at the U of M.
- Personnel will be trained to conduct and document a safety plan and interview. **The IMM and the PI will review the safety plans after the conclusion of the 1st main interview.**

[figure not shown]

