H2.1: Lower affect dysregulation and abnormal self-processing behavior will follow active compared to Unrelated-NF, mediated by amygdala or dACC to mPFC FC changes in self-processing and affect regulation tasks. Bayesian mediation models will test the role of dACC or amygdala-mPFC FC changes on the relationship between NF and affect dysregulation and self-processing behaviors (ETB and IAT)⁶³. The outcome will be the behavioral change (ETB, IAT). The 1st linear model will be one used for H1.2, to test the relationship between the change in FC parameters and behaviors. For the 2nd linear model, the primary predictor will be the indicator term for the NF group, to establish the relationship between NF and behavioral change. Finally, in a 3rd model, the primary predictors will be indicator terms for the NF group, the change in FC parameters, and the interaction between them, to quantify the degree to which NF modifies the relationship between the change in FC parameters and behavioral change.

H2.2: Higher amygdala or dACC to mPFC FC after NF will be associated to lower suicide ideation. Bayesian linear model will use suicide ideation as the outcome, (C-SSRS, SIQ scores) and change in dACC or Amygdala-mPFC FC parameters in the ESOM and the ER tasks as the primary predictors.

H2.3: Affect dysregulation or abnormal self-processing behavioral changes will mediate the association between changes in FC and suicide ideation changes after versus before NF. Bayesian mediation models will test the direct and indirect effect of NF on suicide ideation, but this time we have two mediators: the neural targets and affect dysregulation or abnormal self-processing behavioral scores (ETB and IAT)^{63,64}. These mediators will interact, as we proposed in H2.1. We will fit a Bayesian mediation model with multiple mediators but this time with suicide ideation as the primary outcome, to quantify the direct and indirect effects of NF on suicide ideation change, with each of the change in FC parameters, affect regulation and self-processing behavior as potential mediators. We will fit another model that contains these mediation models as sub-models, i.e., a linear model with the NF indicator as primary predictor, each of the main effects for the change in FC and behavioral change, and an interaction term between the change in FC parameters and behavioral change.

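### H2.2 does not say which C-SSRS score, look-back window or visit is the suicide ideation outcome, omits baseline ideation as a covariate, and leaves attempts without a model

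*Combined protocol and SAP*

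**What the plan says.** **Model.** Section 18, R33 Aim 2, H2.2: a "Bayesian linear model will use suicide ideation as the outcome, (C-SSRS, SIQ scores"). The primary predictors are changes in dACC or amygdala to mPFC FC in the ESOM and ER tasks. H2.3 takes change in suicide ideation as the outcome of a mediation model. Neither names a C-SSRS item, range, look-back window or visit.

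**Role.** Section 3.1 makes the C-SSRS and SIQ R33 primary outcomes "to test changes in suicide ideation and attempts". The R33 models in Section 18 (H1.1 to H2.3) include none for attempts.

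**Scoring.** Section 16.4, item 2 of the inclusion and re-enrolment list, admits "Any suicide ideation severity yielded by the (C-SSRS, ⁴⁹), Scores 0-5". It then prints one numbered list. Categories 1-5 are ideation. The list continues with "Category 6 – Preparatory Acts or Behavior" and reaches "Category 9 – Actual Attempt (non-fatal") and a fatal attempt at 10. Section 16.5 uses wording that crosses the boundary: scores of 4 or 5 "or higher in the C-SSRS (Category 4 - 6").

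**Covariates.** The Data Analysis Plan in Section 18 lists puberty, illness or depression (BDI) severity, treatment indexes, substance use, IQ, handedness and any variable that differs between key groups. Baseline SIQ and baseline C-SSRS are not named.

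**Size and timing.** Section 1: "70 suicide attempting participants with pre-NF assessments will be randomized 1:1 to" active or Unrelated-NF. Table 1 schedules the C-SSRS at Visits 1, 4 and 5, and the SIQ at every visit.

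**The concern.** The ideation outcome can be built in more than one way from the same data, and the plan does not choose. Two analysts could take the 0-5 severity score or the 0-10 category, a lifetime or a recent window, and Visit 4 or Visit 5, and each could say that the plan was followed.

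The choice of score matters in this population. R33 enrols participants who have attempted suicide, and Section 16.1 expects further attempts during the study. On a 0-10 score in a linear model, a non-fatal attempt counts as nine units of ideation. On a 0-5 score it does not enter at all, and the attempts part of the Section 3.1 outcome then has no planned analysis. Each reading leaves a gap.

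The missing baseline term is a separate loss. Ideation after training depends partly on ideation before it, and both scales are already measured at Visit 1.

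**Working it through.** The documents give no power, SD, effect size or attempt rate for H2.2, so there is no plan figure to reproduce. The checks below use n = 70 from Section 1. Everything else is assumed and is marked as such.

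**1. Share of variance from attempts, if 0-10 were analysed.** Let k of 70 participants be coded 9, p = k/70, with ideation mean m and SD s in the rest.

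Share = p(1-p)(9-m)² / [p(1-p)(9-m)² + (1-p)s²]

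For k = 3, m = 2, s = 1.5 (assumed):
- p = 0.0429 and p(1-p) = 0.0410
- attempts: 0.0410 × 49 = 2.01
- ideation: 0.957 × 2.25 = 2.15
- share = 2.01/4.16 = 0.48

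| Attempts coded 9 | m=2, s=1.5 | m=2.5, s=1.3 | m=3, s=1.2 |
|---|---|---|---|
| 1 | 24% | 26% | 26% |
| 2 | 38% | 42% | 42% |
| 3 | 48% | 52% | 52% |
| 5 | 61% | 64% | 64% |
| 7 | 69% | 71% | 71% |

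**2. Effect on the FC association.** Simulation, 4,000 runs per cell: FC change has an assumed correlation of -0.3 with underlying ideation, which is rounded and limited to 0-5 (mean about 2.2, SD about 1.45). The correlation becomes about -0.29. A two-sided 5% Fisher-z test stands in for the Bayesian linear model.

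| Attempts coded 9 | 0-5 score | 0-10, attempts unrelated to FC change | 0-10, attempts in those with highest ideation |
|---|---|---|---|
| 1 | about 0.70 | 0.57 | 0.68 |
| 3 | about 0.70 | 0.41 | 0.63 |
| 5 | about 0.70 | 0.31 | 0.62 |
| 7 | about 0.70 | 0.26 | 0.59 |

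Hand check for three unrelated attempts, with m = 2.2 and s = 1.45 (share 0.485): the correlation shrinks to -0.289 × √(1 - 0.0429) × √(1 - 0.485) = -0.203. Then atanh(0.203) × √67 = 1.68, and power = Φ(1.68 - 1.96) = 0.39, in line with the simulation.

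With no true association, rejection was 0.045 to 0.052 on the 0-10 score, so type I error is not inflated.

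**3. Linear or ordinal on 0-5.** In the same setting, a rank-based or ordinal analysis and the linear one both had power of about 0.69. The ordinal form gained nothing.

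**4. Adjusting for baseline ideation on 0-5.** Assume that baseline and follow-up ideation correlate 0.6 before rounding (0.56 once both are scored 0-5), and that FC change is unrelated to baseline ideation.
- Unadjusted: atanh(0.289) × √67 = 2.44; power = Φ(0.48) = 0.68.
- Adjusted: partial correlation 0.289/√(1 - 0.56²) = 0.349; atanh(0.349) × √66 = 2.96; power = Φ(1.00) = 0.84.

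With an assumed correlation of 0.3 (0.28 as scored), the partial correlation is 0.301 and power is about 0.71. The gain therefore depends on how stable ideation is over the study.

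**The case against.** The strongest reply is that H2.2 calls its outcome suicide ideation and that, where the protocol ties a C-SSRS range to ideation severity, the range is 0-5. The 0-10 list belongs to a suicide-risk section, not to the analysis plan. This stands. A reader might infer that the plan models a 0-10 score and that attempts will therefore overwhelm ideation. No section makes the 0-10 category an analysis variable, and no attempt rate is given. Section 14.1 also temporarily withdraws participants hospitalised for an attempt, which may reduce or delay such codes. Even on 0-10, the loss is small when attempts occur in those with the most ideation.

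A reader might also infer a built-in fall from baseline: attempters start at 9 on a lifetime window and drop on a recent one. That needs both the 0-10 score and unequal windows, and the documents state neither. H2.2 does not say that its outcome is a change score; that wording is in H2.3.

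A third tempting reading is that a linear model is wrong for a six-level score. The check in step 3 does not support this.

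Other mitigations are partial. The SIQ is a co-listed outcome and is unaffected by the scoring question. Section 1 seeks to match participants on ideation where possible, and the covariate clause would admit baseline ideation if it differed between groups. Neither puts it in the H2.2 model as a rule. The planned residual checks and covariate search come after the data, so they do not settle in advance which score is the outcome.

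**Conclusion.** The point holds as under-specification of a primary outcome. H2.2 leaves the C-SSRS score, window and visit open, omits baseline ideation, and Section 18 has no model for the attempts named in Section 3.1. The 0-5 reading is open and likely.

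The cost of the other reading is conditional. With n = 70 and the assumed means and SDs, about three attempts would supply 48-52% of the variance on a 0-10 score. Power at an assumed correlation of -0.3 would fall from about 0.70 to 0.41 if attempts are unrelated to FC change, or from about 0.69 to 0.63 if they track ideation. The harm is lost power and an outcome that is hard to interpret, not false positives. Omitting baseline ideation costs power on any reading in which ideation is stable: about 0.68 against 0.84 at an assumed correlation of 0.6, and little at 0.3.

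**What to change.** In H2.2 and H2.3:

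1. Define C-SSRS ideation as the 0-5 severity score, over the same look-back window at baseline, Visit 4 and Visit 5, and state which visit is primary.
2. Adjust for the baseline score of the same scale: baseline C-SSRS for the C-SSRS outcome, baseline SIQ for the SIQ outcome.
3. Report behaviour and attempts (categories 6-10 since the last visit) as a separate yes/no outcome. With 70 participants this will be largely descriptive, but it gives the attempts part of Section 3.1 an analysis.
4. Keep the linear model. A cumulative-logit model for the 0-5 score is a reasonable sensitivity analysis.

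The cost is a few sentences in Section 18 and one covariate in each model. Table 1 already schedules both scales at these visits. The one condition is that the C-SSRS records keep item-level answers and the recent window separately at Visit 1; if they do not, the form needs that field.

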Data Analysis Plan. SPM12 ⁵⁵ will be used for fMRI statistical analyses. EPI time series' preprocessing will include: (1) realignment for motion correction, (2) slice timing correction, (3) co-registration of EPI with anatomical data, (4) spatial normalization to MNI anatomical, and (5) spatial smoothing. Head motion outliers in EPI time series will be corrected using the Artifact Detection Tools with a scan-to-scan movement threshold of 0.2 mm and a scan-to-scan global signal change of 3 SD ⁵⁶. Activity. For each subject, BOLD activity contrast signal variance will be modeled with regressors using a General Linear Model (GLM) to generate 1st level contrasts (NF vs. CB and NF vs. Rest) for the ESF-NF task similar to procedures followed by Young et al. ³². [name] will lead activity analyses. Connectivity. Time series in dACC or right-amygdala for the ESOM and ER tasks will be used to yield general psychophysiological interaction (gPPI) contrast variables ⁵⁷. The gPPI variables represent FC differences for 'self' vs. 'other' faces recognition or 'regulation' vs. 'passive' viewing. The processing pipeline configuration will be available online. The research staff and a software programmer will generate automatic pre-processing scripts using pilot adult data to yield 1st level images for both activity, connectivity, and structural data to ensure rapid quality control and data access. General PPI analyses yield information flow between neural nodes without direction of exchange. Competing models of affect valuation versus affect modulation/suppression assume 'bottom-up' influence from amygdala on mPFC or 'top-down' influence from the mPFC and dACC on the amygdala, respectively⁵⁸. Dynamic causal modeling (DCM)⁵⁹⁻⁶¹ will follow up gPPI analyses to test bottom-up vs. top-down models of information flow between target neural hubs. DCM will also test FC patterns during NF training but increase target activity during NF is the key target for our Milestone 1. [name] will conduct FC analyses and determine how functional neuro-architecture of affect regulation and self-processing changes after NF training. Defining ROIs. In line with our focus on amygdala, dACC, and their connectivity with mPFC, we will target the dACC (MNI: x=-8, y=30, z=30), the highest loci of activity within the ACC in our pilot results and the right amygdala (MNI x=28 y=0 z=-19), the loci of our amygdala-ACC FC results in attempting participants ⁴¹. ROIs of activity (5 mm) centered in those coordinates during NF, and their FC to mPFC (polar aspects of BA10-9) during ER and ESOM tasks are the target ROIs. The unrelated locus is the left horizontal segment of the intraparietal sulcus (MNI x=-42 y=-48 z=48). This region is not involved in emotion regulation or self-processing and has been used before as a locus of Unrelated comparison NF ^{32,34-36}. Finally, our decision of using specific coordinates, instead of localizing ROIs with a task that elicits dACC or amygdala activity, is supported using pre-determined coordinates for NF in research that yielded ROI up-regulation and symptoms improvement ^{32,34-36}. Accordingly, we have selected coordinates based on our published and pilot work. Puberty ⁵¹, illness or depression (BDI) severity, treatment indexes, substance use, IQ, handedness, or any variable differing between key groups will be covariates in all analyses.

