Bayesian Analyses in the R33 phase will use weakly informative priors using effects reported in the literature. Priors are a key strength of Bayesian models as they allow use of prior information to regularize models, e.g., using R61 phase results to adjust models in the R33 phase. This will boost statistical power since data from both phases will be used. Posterior distributions for model parameters will be constructed by combining priors with the likelihood function from the data. Markov Chain Monte Carlo (MCMC) procedures will be used to obtain samples from the posterior distributions for statistical inference. The Bayesian estimation will be implemented using custom R code in addition to the R package “BEST v0.4.0”^{65,66}.

Model selection and performance. In each of the Aims, we will start with baseline statistical model described above and improve the model by considering potential covariates that will allow the model to fit the data better and improve interpretability and predictive power. We will conduct a thorough search of potential statistical models that might improve on each of our baseline models. We will use residual analyses to assess how well each model fits the data and compute Bayes Factors to quantify quality of statistical models and use predictive cross-validation to assess the predictive capability of each model.

Data Integrity: The key scientific premise of this proposal is that improvement in emotion regulation and self-processing entail quantifiable changes in dACC and amygdala circuits. This proposal is aligned with the 2019 NIMH Strategic Plan 3.2: Develop ways to tailor new interventions to optimize outcomes and responds to the RFA MH-18-704: Development of Psychosocial Therapeutic and Preventive Interventions for Mental Disorders. Rigorous elements of the experimental design include: (a) using a specific threshold of

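### H2.2 leaves the form and timing of the ideation outcome open and does not commit to baseline ideation or trial arm as covariates

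*Combined protocol and SAP*

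**What the plan says.** Section 18, R33 Aim 2, states H2.2 as: "Higher amygdala or dACC to mPFC FC after NF will be associated to lower suicide ideation". The model is one sentence: "Bayesian linear model will use suicide ideation as the outcome, (C-SSRS, SIQ scores) and change in dACC or Amygdala-mPFC FC parameters", which goes on "in the ESOM and the ER tasks as the primary predictors". No visit is named, the outcome is not described as a score or a change, and neither baseline ideation nor the NF indicator appears.

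Four other places bear on this.

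- **General covariates** (Section 18, Data Analysis Plan): after puberty the list runs "illness or depression (BDI) severity, treatment indexes, substance use, IQ, handedness, or any variable differing between key groups will be covariates in all analyses". Baseline SIQ, baseline C-SSRS and arm are not named.
- **Model search** (Section 18, Model selection and performance): the analysts will start from each stated model and "improve the model by considering potential covariates that will allow the model to fit the data better".
- **Design** (Section 1): "70 suicide attempting participants with pre-NF assessments will be randomized 1:1 to" the two conditions, and "Participants will be matched in sex, age, IQ, illness severity, suicide ideation, and abuse history if possible". Ideation is listed separately from illness severity.
- **Measurement** (Section 5, Table 1 and the study item table): SIQ is taken at Visits 1 to 5, and C-SSRS at Visits 1, 4 and 5.

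The neighbouring models are fuller. H1.2, the second and third H2.1 models and the closing H2.3 linear model name the NF indicator. H2.1 uses behavioural change as its outcome, and H2.3 refers to change in ideation. Section 3.1 says the R33 ideation scales serve to test changes.

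**The concern.** Ideation before training is likely to predict ideation afterwards. Leaving it out of a regression on the later score gives up precision in a trial of 70.

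There may also be bias. Connectivity (FC) change contains pre-NF connectivity. Section 5 (ESOM task) says that ACC-amygdala connectivity distinguishes suicide attempters from depressed and healthy adolescents, so a link between starting ideation and FC change is plausible, though not shown. Sections 8.1 and 9 admit a wide range of starting ideation. If such a link exists and ideation is analysed as a level, the regression can show the negative association that H2.2 predicts with no effect of FC change on ideation.

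Arm is a second route. If active NF raises FC change and lowers ideation by some other path, pooling the arms without the indicator mixes the between-arm contrast with the within-arm association.

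Ideation is an R33 primary outcome, so an undefined outcome form in this model matters in its own right.

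**Working it through.** The documents give no power, slope, alpha or baseline-to-post correlation for H2.2, so there is no stated figure to reproduce. From the documents: N = 70, 1:1, hence 35 per arm. Everything else below is assumed. Let r be the correlation of baseline with post-NF ideation (equal variances) and c the correlation of baseline ideation with FC change.

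**1. Precision, outcome read as the post-NF score.** If c = 0, baseline adjustment removes r² of the outcome variance. The slope standard error is multiplied by √(1 - r²), and the equivalent unadjusted sample is 70/(1 - r²). The comparison is a model with no covariates.

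| r | variance removed | SE multiplier | equivalent N |
|---|---|---|---|
| 0.3 | 9% | 0.95 | 77 |
| 0.5 | 25% | 0.87 | 93 |
| 0.6 | 36% | 0.80 | 109 |
| 0.7 | 49% | 0.71 | 137 |

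Unadjusted, N = 70 detects a correlation of tanh[(1.96 + 0.84)/√67] = 0.33 with 80% power (two-sided 0.05).

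**2. Precision, outcome read as a change score.** The change score has variance 2(1 - r) and the baseline-adjusted residual 1 - r². Their ratio gives an equivalent N of 70 × 2/(1 + r) = 140/(1 + r), which is 93 at r = 0.5 and 82 at r = 0.7.

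**3. Bias, post-NF score.** With no true FC effect and no arm effect, the induced correlation is r × c. At r = 0.6 and c = -0.3 it is -0.18. Fisher z: 0.182 × √67 = 1.49, and P(Z > 1.96 - 1.49) is about 0.32.

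**4. Bias, change score.** The covariance of ideation change with FC change is (r - 1) × c = (-0.4)(-0.3) = +0.12. The SD of change is √0.8 = 0.894, so the correlation is about +0.13, opposite in sign to the hypothesis.

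**5. Simulation, post-NF score.** 35 per arm, 5,000 runs per scenario, r = 0.6, no true FC effect, least squares standing in for the Bayesian linear model, two-sided 0.05. In the shift rows active NF raises FC change and lowers ideation, in SD units. The proxy is a BDI-like measure correlating 0.6 with baseline ideation. Cells show the percentage of runs declaring an association.

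| scenario | FC change only | + arm | + baseline | + both | + proxy only |
|---|---|---|---|---|---|
| c = 0, no shifts | 4.8 | 4.6 | 4.6 | 4.7 | 4.7 |
| c = 0, shifts 0.5 and 0.5 | 7.3 | 5.1 | 9.1 | 4.3 | 8.1 |
| c = 0, shifts 0.8 (FC) and 0.5 | 11.9 | 4.7 | 15.5 | 4.6 | 12.5 |
| c = -0.2, no shifts | 17.2 | 16.5 | 4.8 | 5.0 | 10.4 |
| c = -0.3, no shifts | 32.3 | 31.7 | 5.1 | 5.0 | 18.0 |
| c = -0.2, shifts 0.5 and 0.5 | 30.8 | 17.1 | 9.2 | 5.1 | 21.2 |
| c = -0.3, shifts 0.5 and 0.5 | 48.2 | 32.2 | 9.5 | 5.0 | 31.6 |

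Neither term alone is enough when both routes operate. With both in the model the rate stays between 4.3% and 5.1%.

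**The case against.** **The outcome may already be a change.** Section 3.1 speaks of testing changes, and H2.3 uses plain suicide ideation and its change almost interchangeably. A reader might infer that H2.2 certainly analyses the post-NF score. The documents do not establish that, and under the change reading the bias turns positive and the precision gain is smaller. This stands. It does not clear the model, because a change score left unadjusted for baseline can mask a true effect, and the ambiguity remains.

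**Covariates are provided for.** A reader might infer that H2.2 is fitted on FC change alone. Section 18 calls FC changes the primary predictors, not the only terms, applies a covariate list to all analyses and allows a search for more. So the no-covariate figures are an upper comparison. But a variable qualifying because it differs between groups says nothing about a link within arms, and neither does matching where feasible. A severity covariate helps only in part (32% to 18%). A search guided by fit is not a prior commitment.

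**H2.3 already puts arm and FC change in one ideation model.** True, but that model also conditions on behavioural change, names no baseline ideation and does not test H2.2. Pooling arms can be a deliberate choice of overall association; if so, the plan should say so.

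**The 32% is one chosen point.** Correct. No document supports c = -0.3, and at zero the rate is nominal. It is also a two-sided 0.05 rate applied to a Bayesian model for which no decision rule is stated.

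**Conclusion.** The point holds as a gap in specification with a conditional cost. H2.2 does not fix the outcome's visit or form, and nothing in Section 18 guarantees that baseline ideation or arm enters the model.

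The precision argument needs only that baseline and later ideation correlate. The bias argument also needs starting ideation to correlate with FC change, or NF to move both FC change and ideation by separate paths. Omitting arm is the lesser problem on its own. It would go too far to say that H2.2 is biased towards confirmation: the documents give neither the correlations nor the outcome form that this would require, and the sign of the bias depends on that form.

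The change should be made because it protects under either reading and uses data already scheduled. The trial remains feasible without it.

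**What to change.** In Section 18, H2.2:

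- State the outcome as the post-NF SIQ score, and separately the C-SSRS score, at one named visit.
- Include the Visit 1 value of the same scale and the NF indicator as fixed covariates alongside FC change, outside the model search.
- Use the same baseline adjustment in the H2.3 ideation model.

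No new data are needed. The cost is a sentence or two in the analysis plan and at most two degrees of freedom per model.
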